#### **11.2 Follow-up Schedule**

- **11.2.1** Initial follow-up visit at 2 weeks then 1, 3 and 6 months from start of treatment.
- **11.2.2** VAS will be measured at 2 weeks, 1, 3, and 6 months and then every 6 months for 3 years by research staff. VAS will be measured on the day of treatment and weekly there after for 5 weeks by patient diary.
- **11.2.3** BPI, Fact-G, and EQ-5D will be done at baseline, 1, 3, 6, and 12 months post therapy.
- **11.2.4** After initial follow-up visits, follow-up will be done at 6 month intervals post therapy for 3 years.
- **11.2.5** MRI at baseline, 1, 3, 6 and then every 6 months for three years. These MRI are to be done of the treated level and a complete whole spine MRI will be done when clinically indicated based on pain or other new neurological symptom.

#### 11.3 Criteria for Toxicity

**11.3.1** All acute and late adverse events from protocol radiation therapy will be reported and scored for severity using the NCI Common Terminology Criteria for Adverse Events (CTCAE) version 3.0. A copy of the CTCAE v3.0 can be downloaded from the CTEP home page (http://ctep.info.nih.gov).

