#### Exclusion:

- Patients who have been non-ambulatory for more than 7 days
- Patients with compression fractures

- Spine instability requiring fixation
- Patients with paraspinal extension
- Patients with bony fragments
- Planned systemic treatment within one week after treatment.
- Absence of pathological diagnosis of cancer
- Chemotherapy within one week of treatment
- Patients with Multiple Myeloma, Lymphoma, or Plasmacytoma
- Patient suffered from unstable angina and/or congestive heart failure requiring hospitalization within the last 6 months
- Patient had a transmural myocardial infarction within the last 6 months
- Patient has an acute bacterial or fungal infection requiring intravenous antibiotics at the time of registration
- Patient has hepatic insufficiency resulting in clinical jaundice and/or coagulation defects
- PT is not within normal limits or planned and feasible to be corrected to normal limits prior to vertebroplasy
- PTT is not within normal limits or planned and feasible to be corrected to normal limits prior to vertebroplasy
- Platelet count is < 50,000
- History of significant psychiatric illness

Vertebroplasty may not be possible for certain patients due to tumor location or safety. In such cases, patients will omit the vertebroplasty but receive all other protocol care and follow-up. Visual Analog Scoring

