The initial complication rate of vertebroplasty in patients with metastatic disease is reported to be approximately 10%[23]. This is significantly higher that observed when the procedure is done for osteoporotic compression fractures (2-5%). This is likely secondary to increased bony destruction in the cancer patient. Reported complications include cement leakage into the spinal canal, neural foramina or paraspinous soft tissue. Notably, most cement leaks are asymptomatic and the long term complication rate is reported to be 1.7%. Cement leakage into the neural foramina can cause a painful radiculopathy which typically improves spontaneously in most patients. Extravasation into the spinal canal can cause spinal cord compression. In some instances surgery to decompress the neural structures was necessary. Extravasation into the epidural venous plexus or inferior vena cava can result in pulmonary embolism[26]. Increased back pain after the procedure has also been reported and is thought to be secondary to local irritation from the PMMA. This typically responds well to a short course of non-steroidal anti-inflammatory medications[25].

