#### 6.10 Radiation Adverse Events

6.10.1 Neurology

Monitored treatment related toxicity associated with neurology function will include myelitis, motor and sensory neuropathy, plexopathy, and pain. The consequences of neurology toxicity should all be graded according to the Common Terminology Criteria For Adverse Events (CTCAE).

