#### 6.11 Serious Adverse Event Reporting

6.11.1 ERGO

Electronic Research Grant Organizer (ERGO) constitutes a mechanism for reporting serious adverse events to the UTSW IRB for reporting purposes.

Any adverse event equivalent to CTCAE V.3 grade 3, 4, or 5 or which precipitates hospitalization or prolongs an existing hospitalization must be reported regardless of designation (expected or unexpected) along with the attribution. This includes all deaths that occur within 30 days after the patient was discontinued from the study regardless of attribution AND any events that occur beyond 30 days and are considered probably related to treatment.

Participating sub-sites must file an SAE report (the CRF plus information describing the event, the grade, and the attribution) within 48 hours of the investigator's awareness of the occurrence of the event.

Attribution of an event can be categorized as:

- Not Related
- Possibly Related
- Likely Related

Adverse events (below grade 3) do not need to be submitted immediately. Rather, they should be documented in the Adverse Events CRF along with a brief description of the event, grade, and attribution).

All SAE reports should be made via FAX transmission to:

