#### 8.0 Surgery:

8.1 Vertebroplasty

Vertebroplasty will be performed within one month of start of radiation therapy in the standard angiography suite or in the operating room depending on individual patient needs. C-arm fluoroscopy will be utilized for localization and visualization throughout the procedure. All patients undergo continuous physiologic monitoring and observation by anesthesia provider. In most instances the procedure may be completed using conscious sedation with a combination of a short acting narcotic and benzodiazepine. Local anesthesia with lidocaine or bupivicaine is also utilized.

The patient will be positioned prone on the operating table, prepped and draped in the usual sterile fashion. Under fluoroscopic guidance, the pedicle of the involved vertebral level is localized. The skin, soft tissue and periosteum are anesthetized. A standard bone biopsy needle with an outer cannula and a central stylet is advanced under fluoroscopic guidance into the vertebral body via the pedicle. The stylet is removed and the polymethyl methacrylate (PMMA) mixture is injected into the vertebral body through the cannula under continuous fluoroscopy. Careful attention to any extravasation is noted. After adequate vertebral body fill, the cannula is withdrawn and a sterile dressing applied to the puncture site.

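### Sections 11.3.1 and 6.10 frame toxicity scoring as radiation-only while 6.11.1 covers any adverse event, so low-grade vertebroplasty events may be captured unevenly, and attribution does not separate the two components

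*Combined protocol and SAP*

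**What the plan says.** **Radiation-specific text.** Section 11.3.1, the criterion for toxicity, states that "All acute and late adverse events from protocol radiation therapy will be reported and scored for severity" under CTCAE version 3.0. The organ-by-organ lists are headed "6.10 Radiation Adverse Events". They name no cement leakage, extravasation or pulmonary embolism, although 6.10.1 does name neuropathy and pain.

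**Vertebroplasty as a protocol treatment.** Section 8.1 states: "Vertebroplasty will be performed within one month of start of radiation therapy". Footnote 1 to the Schema's eligibility criteria allows exceptions: "Vertebroplasty may not be possible for certain patients due to tumor location or safety". Those patients stay on study with all other care and follow-up. Section 1.3 gives the expected harm: "The initial complication rate of vertebroplasty in patients with metastatic disease is reported to be approximately 10" per cent. It adds that "most cement leaks are asymptomatic and the long term complication rate is reported to be 1.7" per cent.

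**General text.** Section 6.11.1 states: "Any adverse event equivalent to CTCAE V.3 grade 3, 4, or 5 or which precipitates hospitalization or prolongs an existing hospitalization must be reported". It sets no limit by cause, and it sends events below grade 3 to the adverse event CRF with a description, grade and attribution. Section 6.10.7 has a catch-all for other treatment-related toxicity. The adverse event row in Appendix I is not restricted by cause.

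**Attribution.** Section 6.11.1 lists three levels: Not Related, Possibly Related and Likely Related. They refer to treatment, with no component named. The same section extends reporting to "any events that occur beyond 30 days and are considered probably related to treatment".

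**The concern.** The trial tests a combination, and its safety data should describe both parts. The section that sets the toxicity criterion, and the lists that tell a site what to look for, mention only one part. A site working from 11.3.1 could reasonably leave out a small asymptomatic leak because it did not come from radiation. A site working from 6.11.1 would enter the same leak on the CRF. The observed rate of minor cement events would then depend partly on site practice.

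The second issue is attribution. Patients who omit vertebroplasty receive SBRT alone but are followed in the same groups. If an event is attributed only to treatment, the final tables cannot say which component caused it. The safety committee in Section 14.0 re-examines attribution, but it works from what was reported and on the same undivided scale.

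The third issue is small. The late-event clause uses the word *probably*, which is not one of the three levels on the scale.

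**Working it through.** The plan gives no calculated figure on this point, so the check is a comparison of sections followed by arithmetic for scale.

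**Step 1. Follow three kinds of vertebroplasty event through the text.**
- *Grade 3-5 or hospitalizing event* (for example, cord compression needing surgery): outside the wording of 11.3.1, but inside 6.11.1. It is reported whatever its cause.
- *Low-grade symptomatic event* (for example, radiculopathy or procedural pain): outside 11.3.1. The terms neuropathy and pain appear in 6.10.1, under the radiation heading. Section 6.11.1 sends the event to the CRF.
- *Asymptomatic leak or extravasation*: outside 11.3.1 and on no list. Section 8.1 asks that extravasation be noted, but does not say where it is recorded. Section 6.11.1 captures it only if the site treats it as an adverse event.

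The sections therefore agree on serious events only through 6.11.1, and they diverge below grade 3. The asymptomatic leak is the most exposed. Section 12.1 does not settle the matter: it lists SBRT dosimetry but no vertebroplasty record, and it times adverse event assessments from SBRT.

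**Step 2. Scale.**
- Planned patients (Schema; Sections 13.1 and 13.2): 29 + 13 = 42.
- Cited initial complication rate (Section 1.3): 0.10.
- Share having vertebroplasty: not given. I assume 50% to 100%.

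Expected initial complications = number having the procedure × 0.10:
- 100%: 42 × 0.10 = 4.2
- 75%: 0.75 × 42 = 31.5, taken as 32; 32 × 0.10 = 3.2
- 50%: 21 × 0.10 = 2.1
- Both groups stop after stage 1 and all have the procedure: (9 + 6) × 0.10 = 1.5

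At the cited long-term rate of 1.7%, 42 × 0.017 = 0.7.

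The chance that at least one initial complication occurs is 1 − 0.9^n: 0.988 for n = 42, 0.97 for n = 32 and 0.89 for n = 21. This is the chance of occurrence. The documents give nothing from which a chance of non-recording could be calculated.

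**Step 3. The late-event clause.** The main rule in 6.11.1 has no time limit and no attribution threshold. The 30-day clause is introduced as part of that rule, and its clock runs from discontinuation from the study. Patients are followed for 3 years (Section 11.7). A late grade 3-5 event in a patient still on study is therefore reportable without reference to *probably*. The term matters only for events more than 30 days after discontinuation. There, the nearest level on the scale is Likely Related, but the text does not equate the two.

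**The case against.** The strongest reply is that the general rule already does the work. Section 6.11.1 covers any adverse event at every grade, 6.10.7 adds a catch-all, Appendix I schedules adverse event evaluation without regard to cause, and the safety committee reviews all that is reported. On that view 11.3.1 is one clause worded too narrowly. This stands for serious events. It does not fully stand for minor ones, because 11.3.1 is the section headed as the toxicity criterion, and 6.10.7 itself sits under the radiation heading.

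A reader might infer that adverse event collection is limited to radiation, or that most vertebroplasty events would be lost. The documents do not support either. A reader might also take the 99% chance of at least one complication as a measure of the defect. It counts complications expected to occur, not complications missed, and it assumes that every patient has the procedure.

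A third tempting inference is that late related events could go unreported throughout follow-up. Step 3 shows that the clause applies only after study exit. A Possibly Related event that fails a *probably* threshold is what a threshold does. It is not a gap.

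Finally, the CRF is not among the documents. It may already contain fields for vertebroplasty events or for attribution by component. If so, the protocol text still needs to match it.

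**Conclusion.** The point holds as an inconsistency and a limit on interpretation. Sections 11.3.1 and 6.10 are radiation-specific, while 6.11.1 is general. Serious vertebroplasty events would be reported. Low-grade and asymptomatic cement events could be recorded unevenly. As far as the documents show, toxicity cannot be assigned to radiation or to vertebroplasty, although some patients receive only the former.

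The number of events exposed is about 4 if all 42 patients have the procedure, and about 2 to 3 if 50-75% do. This rests on the cited 10% rate, on full accrual and on the assumed uptake. Section 1.3 does not say whether the 10% includes asymptomatic leaks. In a trial of this size, a few events recorded differently between sites would visibly change the toxicity table. The primary pain analysis and the sample size are not affected.

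The mismatch between *probably* and the attribution scale is a genuine but minor wording fault.

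**What to change.** 1. In 11.3.1, widen the scope to events *from protocol radiation therapy or vertebroplasty*.
2. Add cement leakage or extravasation and pulmonary embolism to the monitored events, under a heading not confined to radiation. Neuropathy and pain are already named in 6.10.1 and need only apply to both components.
3. Record attribution separately for radiation and for vertebroplasty. Record whether vertebroplasty was done, so that toxicity can also be tabulated by treatment received.
4. In 6.11.1, reconcile the late-event term with the stated scale, for example by using *likely related*. Extending the trigger to possibly related events would lower the reporting threshold. That is the sponsor's choice, not a correction.

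The cost is a wording amendment, extra CRF fields if they do not already exist, and a few more low-grade events to record. No treatment, visit or sample size changes.

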## Please note that this study will not be using separate toxicity scales for acute and late radiation adverse events.

#### 11.4 Measurement of Pain Response

- **11.4.1** Pain as the primary endpoint of the study will be assessed by VAS at 1 month by research staff.
- **11.4.2** Pain will also be assessed by VAS at 2 weeks, 1, 3, and 6 months and then every 6 months for 3 years post therapy by research staff. A patient pain diary of maximum VAS of treated spine recorded on the same day of radiation treatment and then weekly for 5 weeks following radiation treatment.
  - **11.4.2.1** Response to pain will be scored as Complete Response (CR), Partial Response (PR), or other.
  - **11.4.2.2** Complete response (CR): defined as a score of 0 on the VAS at the treated site with no increase in narcotic requirements
  - **11.4.2.3** Partial response (PR): defined as an improvement of at least two points on the VAS with no increase in narcotic requirement.
  - **11.4.2.4** Other will include people with stable pain, increasing narcotic requirements, and progressive pain

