#### 2.2 Secondary:

- 2.2.1 To determine the duration of pain response at the treated site(s) scored as the time of maximal pain relief to an increase of 2 on the VAS
- 2.2.2 To determine the functional preservation of improvement using the Brief Pain Inventory (BPI)
- 2.2.3 To prospectively assess patients quality of life (QOL) using the Functional Assessment of Cancer Therapy General (FACT-G) and patients utilities using the EuroQol (EQ-5D)
- 2.2.4 To determine the long term stability of the treated vertebral bone (such as fracture, sclerotic change, vertebral body height or mal alignment) by MRI, CT scan and plain radiographs.

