#### **11.6 Other Response Parameters**

- **11.6.1** Duration of Pain Response: The duration of pain response will be measure from the date that CR or PR was recorded to the date of increase in the VAS at the treated site to a score 2 points higher than the lowest VAS score recorded.
- **11.6.2** Time to Functional Decline: Time from study entry to a Zubrod  $PS \le 3$
- **11.6.3** Overall Survival: The survival time will be measured from the date of accession to the date of death. All patients will be followed for survival. Every effort should be made to document the cause of death.

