#### 11.7 Removal of Subject from Study

We will be following the patients for 3 years. Subjects can be taken off the study treatment and/or study at any time at their own request, or they may be withdrawn at the discretion of the investigator for safety, behavioral or administrative reasons. The reason(s) for discontinuation will be documented and may include:

- 11.7.1 Subject voluntarily withdraws from consent
- 11.7.2 Subject is unable to comply with protocol requirements.
- 11.7.3 Subject demonstrates disease progression to targeted site.
- 11.7.4 Subject experiences toxicity that makes continuation in the protocol unsafe.
- 11.7.5 Development of second malignancy that requires treatment, which would interfere with this study.
- 11.7.6 Treating physician judges continuation on the study would not be in the subject's best interest.
- 11.7.8. Subject becomes pregnant.
- 11.7.9 If a research subject cannot be located to document survival after a period of 2 years, the subject may be considered "lost to follow-up". All attempts to contact the subject during the two years must be documented and approved by the Data Monitoring Committee.

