#### **13.0 Statistical Consideration**:

#### 13.1 Single Fraction Treatment Group

#### **Two-Stage Design and Sample Size Justification**

The planned sample size of 29 total eligible subjects is based on Simon two-stage optimal design with an overall significance level of 0.05 and power of 90% (Simon R, 1989). The concept of this design is to permit early stopping when a moderately long sequence of initial failure occurs. The historical response rate to conventional radiation treatments is 50%[27]. This response rate comes from the RTOG 9714 trial which looked at 800 cGy in one fraction vs 3000 cGy in ten fractions. It represents combined complete and partial responses. This trial set the standard of care for

palliation of pain bone metastasis in previously unirradiated patients and thus is used as the historical control for this group. The statistical hypothesis tested is as follows:

H0:  $p \le 50\%$  vs. HA:  $p \ge 80\%$ , where p is one month pain response rate

Rejection of  $H_0$  means that further study of the test treatment should be carried out. Under the above hypotheses, the type I error is the false-positive rate in accepting an ineffective treatment and type II error is the false-negative rate in rejecting a promising treatment.

Stage 1 of the study will include 9 eligible subjects. If at least 6 of 9 eligible subjects respond, an additional 20 subjects will be enrolled into stage 2 of the study. If the total number of patients who respond (among the 29 patients) is 19 or more, the null hypothesis above will be rejected in favor of the alternate hypothesis.

Under the null hypothesis ( $p \le 50\%$ ), the expected sample size of the trial is only 14.

The assumptions and specifications for Simon's two-stage design are detailed in the following table 1

Alpha -----> 0.05

Beta -----> 0.10

Response Probability of Historical Conventional Radiation Treatment (P0) ---> 0.5 Response Probability of Stereotactic Radiation Treatment (P1) ---> 0.8

Optimal Two Stage Design	Optimum Design
First Stage Sample Size (n1)	9
Upper Limit For 1st Stage Rejection of Stereotactic	
Radiation Treatment (r1)	5
Maximum Sample Size (n)	29
Upper Limit for 2nd Stage Rejection of Stereotactic	
Radiation Treatment (r)	18
Expected Sample Size If Response Probability = P0	14.08
Probability of Early Termination at P0	0.75

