#### **13.3 Secondary Endpoints**

Secondary endpoints will be analyzed by the following methods. For overall survival Kaplan-Meier plots and median times will be reported. Time to functional decline will me measured with Kaplan-Meier plots and median times will be reported. Duration of pain response will be measured with Kaplan-Meier plots and median duration of pain response will be reported.

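### Median duration of pain response is set by the VAS visit spacing: relapse is interval-censored, but Section 13.3 plans an ordinary Kaplan-Meier median

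*Combined protocol and SAP*

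**What the plan says.** **Measurement.** Section 11.4.2 sets the staff schedule: "Pain will also be assessed by VAS at 2 weeks, 1, 3, and 6 months and then every 6 months for 3 years". Section 11.2.2 gives the same times. The patient diary adds a weekly maximum VAS, "recorded on the same day of radiation treatment and then weekly for 5 weeks following radiation treatment". From week 5 on, the scheduled readings are at months 3, 6, 12, 18, 24, 30 and 36. Section 11.7 confirms the horizon: "We will be following the patients for 3 years".

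**Start of duration.** Section 11.6.1 counts "from the date that CR or PR was recorded". Objective 2.2.1 describes the same quantity as "scored as the time of maximal pain relief to an increase of 2 on the VAS". These are different starting points.

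**End of duration.** Section 11.6.1 runs "to the date of increase in the VAS at the treated site to a score 2 points higher than the lowest VAS score recorded".

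**Analysis.** Section 13.3: "Duration of pain response will be measured with Kaplan-Meier plots and median duration of pain response will be reported". It plans the same kind of analysis for time to functional decline. The plan gives no interval-censored method, no dating convention for relapses between visits and no sensitivity analysis.

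**The concern.** If pain returns between two visits, all that is known is that relapse fell after the last VAS without it and at or before the first VAS with it. An ordinary Kaplan-Meier analysis treats the recorded date as exact. Dating relapse at the visit that reveals it lengthens the response by anything up to the whole gap, and from month 6 the gaps are 6 months.

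Durable pain control is part of the rationale in Section 1.4, and duration of response is the first secondary objective (2.2.1). A median that reflects the calendar as much as the patients would mislead on that property. It would also not compare cleanly with studies that measured pain more often.

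**Working it through.** **1. The plan's own figures.** There is none to reproduce for duration: no expected median, event count or precision is stated. The only design figures concern the primary endpoint, and they reproduce. The 9/29 design gives alpha 0.0477, power 0.905, probability of early termination 0.746 and expected size 14.08. The 6/13 design gives 0.0431, 0.905, 0.647 and 8.47. They set the likely number of responders. "The planned sample size of 29 total eligible subjects" at an 80% response rate gives 29 × 0.80 ≈ 23, and the five-fraction group gives 13 × 0.75 ≈ 10.

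**2. Values the median can take.** With response recorded at time *s* and visits on schedule, a duration ending in relapse equals (visit time − *s*).
- *s* = 1 month: 2, 5, 11, 17, 23, 29, 35.
- *s* = 2 weeks: 0.5, 2.5, 5.5, 11.5, 17.5 and so on.
- *s* = 3 months: 3, 9, 15, 21 and so on.

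Real visit dates will blur these values, but visit timing still sets them.

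**3. Large-sample overstatement.** Let *m* be the true median counted from the recorded start. Reported median = (first visit at or after *s* + *m*) − *s*. Example with *s* = 1 and *m* = 6: 1 + 6 = 7, the next visit is month 12, 12 − 1 = 11, and 11/6 = 1.83. The values of *m* are assumptions.

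| Assumed *m* (months) | *s* = 2 weeks | *s* = 1 month | *s* = 3 months |
|---|---|---|---|
| 3 | 5.5 (+83%) | 5 (+67%) | 3 (0%) |
| 4 | 5.5 (+38%) | 5 (+25%) | 9 (+125%) |
| 6 | 11.5 (+92%) | 11 (+83%) | 9 (+50%) |
| 9 | 11.5 (+28%) | 11 (+22%) | 9 (0%) |
| 12 | 17.5 (+46%) | 17 (+42%) | 15 (+25%) |

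The extremes for *s* = 1 lie at the gaps. A true median of exactly 5 or 11 months gives 0%. A true median of 5.01 gives 11 (+120%), and 2.01 gives 5 (+149%).

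**4. Trial-sized samples.** In simulation I assumed exponential relapse, 23 responders, response at month 1 and median survival of 12 months. The mean overstatement was +63%, +59%, +57%, +45%, +41% and +31% for true medians of 3, 4, 6, 8, 9 and 12 months. At a true median of 6 the typical (median) estimate was 11.0 months.

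Individual estimates can miss low. With 10 responders and a true median of 12, the typical estimate was 11.0 to 11.5 months (−8% to −4%), while the mean was still 12% to 27% too long. With 23 responders, starts split between 2 weeks and 1 month, and survival as above, a true median of 12 gave a typical 11.5 and a mean of 15.0.

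**5. Does interval censoring help?** Take *s* = 1, *m* = 6 and exponential relapse. The proportion still in response is 2^(−5/6) = 0.561 at a duration of 5 months and 2^(−11/6) = 0.281 at 11 months. The median therefore lies between 5 and 11. Linear interpolation gives 5 + 6 × (0.561 − 0.500)/(0.561 − 0.281) ≈ 6.3, against 11 from visit dating.

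In simulated samples of 23, for true medians of 3, 4, 6, 9 and 12 months:
- visit-dated Kaplan-Meier typically gave 5, 5, 11, 11 and 17;
- a Turnbull fit with linear interpolation gave about 3.3, 4.3, 6.5, 9.2 and 12.3, with similar results under a non-exponential relapse pattern.

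At a true median of 6, midpoint dating gave 8.0 and a parametric interval-censored fit gave 5.8 to 6.0.

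**6. The start date matters too.** Suppose partial response is first recorded at month 1, the lowest VAS at month 3, and relapse is seen at month 12. Section 11.6.1 gives 12 − 1 = 11 months. Objective 2.2.1 gives 12 − 3 = 9.

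**The case against.** **Relapse is not literally dated at the visit.** Section 11.6.1 speaks of the date on which VAS increased. This is correct, and an unscheduled reading could supply an earlier date. But no such reading is planned after week 5, so the visit date is what will normally be available. The diary could show a very early relapse, though it records maximum VAS and the plan does not say it counts toward duration.

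**The start is also read at a visit.** This offsets part of the delay, by up to about 2 months for a response first recorded at month 3. It stands as a partial offset only, because later gaps are 6 months.

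**Turnbull mostly returns the visit interval.** This is largely true without interpolation. But that interval is what the data support, and a single figure at its upper end is not. The parametric recovery in step 5 used data generated from the fitted model, so it flatters that fit. The interpolated Turnbull result does not depend on that match.

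**Duration is descriptive and secondary.** This stands. There is no comparator, threshold or decision rule for it, and the one-month primary endpoint is untouched.

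**Stronger readings that the documents do not support:**
- A reader might take the +83% at an assumed 6-month median as a ceiling. It is one point in a range from 0% to about 150%, and the documents give no true median.
- A reader might infer that the planned confidence limits are wrong. Section 13.3 commits to plots and medians and states no limits.
- A reader might expect interval censoring to recover relapses that go unseen because the patient died before the next visit. It does not: those patients stay right-censored at their last VAS.

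**Conclusion.** The point holds as a cheap improvement to a secondary analysis. After week 5 the schedule can place relapse only within gaps of about 2, 3 and then 6 months, and Section 13.3 does not allow for this. The visit-dated median is biased upward on average. The typical overstatement is about 20% to 80% for assumed true medians of 3 to 12 months with response recorded at month 1, with none on a visit gap and more than 100% just past one. In groups of about 23 and 10 responders, one estimate may still fall below the truth.

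These sizes rest on assumed true medians, visits kept on schedule, relapse dated at the visit that shows it and, for the simulated figures, assumed relapse and survival patterns.

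Time to functional decline has the same weakness, since Appendix I schedules performance status at months 1, 3 and 6 and then every 6 months. It has a prior problem: Section 11.6.2 writes the threshold as Zubrod PS ≤ 3, which every eligible patient (0 to 2) already meets at entry.

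**What to change.** 1. **Start date.** Reconcile objective 2.2.1 with Section 11.6.1 first, since the analysis needs one time origin. State whether diary readings count toward duration.
2. **Section 13.3.** Analyse duration of pain response as interval-censored between the last VAS without relapse and the first VAS with relapse, by Turnbull or a parametric interval-censored fit. Right-censor patients without an observed relapse at their last VAS.
3. **Reporting.** Give the median as an interval, and add the proportions still in response at the 3-, 6- and 12-month visits.
4. **Functional decline.** Reconcile the threshold in Section 11.6.2 with the eligibility criteria, then apply the same method.

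The cost is analysis wording and a standard routine, with no new visits or patient burden. The downside is that the reported median becomes shorter and is shown as a range.
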